**Abstract:** Recently there has been compelling evidence that inflammatory bowel disease (IBD) subjects, both Crohn's disease (CD) and Ulcerative Colitis (UC), commonly have disrupted sleep, and disrupted sleep correlates with the risk of disease flare. Sleep/wake cycle, immune function, metabolism and multiple biological processes are all orchestrated by circadian rhythms. Circadian misalignment between the central circadian clock in the brain and environment has been found to contribute to a variety of metabolic and gastrointestinal tract (GIT) diseases. Yet, the prevalence and impact of circadian misalignment on IBD disease activity and GIT mucosal inflammation have not been established. The long-term objective of our research is to investigate the hypothesis that circadian malalignment worsens GIT mucosal inflammation and disease course in IBD. To test this hypothesis, we will conduct a prospective in lab study with human subjects on the impact of circadian misalignment in left sided mild to moderate Ulcerative Colitis. We will perform two circadian measures phase assessments under strictly controlled laboratory conditions at: 1) baseline, and after 2) circadian misalignment after three days of simulated night shifts in both inactive UC patients and healthy control subjects. To test the hypothesis that UC patients (compared to healthy subject controls) are less resilient to circadian misalignment we will assess: time impact of our protocol on circadian rhythms (Aim 1) by the following: phase angle of entrainment [time from dim light melatonin onset to sleep onset] (Aim1a); peripheral circadian rhythms by clock gene expression in colonic tissue from a flexible sigmoidoscopy and in subjects peripheral blood mononuclear cells (Aim1b); and colonic clock gene expression and Per2::Luc activity over 24 hours utilizing an in-vitro model of colonic organoids (Aim1c). Next, we will test the hypothesis that circadian misalignment will increase colonic permeability and mucosal inflammation in UC patients (vs. Controls) (Aim2) through the following: endoscopy score, stool calprotectin, colonic barrier (permeability, AJC proteins), and markers of systemic barrier function and inflammation (Aim 2a); adversely impacting microbial community structure/function (Aim 2b); and use 2D colonic organoid monolayers to explore ex-vivo barrier function by co-culturing with TNF- $\alpha$ /INF- $\gamma$  (Aim

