**Sample Size Analysis:** All power estimates were computed using R package pwr, and we assume a Type I error rate of 0.05 and a 2-sided test for all analyses. Power estimates were derived from the data from my prior K grant. The primary endpoints of this study will be phase angle/DLMO (Aim 1) and colonic permeability (13-24h urinary sucralose) (Aim 2). For Aim 1, we found a  $\sim 2$ h phase advance in DLMO in NW compared to DW at -0.2 (SD=2.1) compared to -4.34 (SD=3.8), respectively. With a sample size of 20 in each group (10 men/10 women), this

provides an 86% power to detect differences in DLMO, but 98% power if sex is pooled. For Aim 2, we found a 40% increase in colonic permeability in night shift workers compared to day workers after moderate alcohol consumption at 0.57 compared to 0.11 (SD=0.20). With 20 subjects, this will give us a 84% power to detect a difference in colonic permeability between the two groups for each sex and if sex is pooled will give us a 97% power with a two-sided two-sample t-test at alpha=0.05 level. These conservative estimates provide a good estimate of the power to detect differences in phase angle and colonic permeability between UC patients before and after simulated night shifts. We anticipate we will have nonparametric data and will use the Wilcoxon match-pair test for analysis of colonic permeability, inflammatory cytokines, and markers of endotoxemia. Order effects will be used as a covariate in multivariate analysis with analysis of variance (ANOVA) and linear regression as indicated. Microbiota data analysis is described above. Non-parametric analysis of actigraphy data will be analyzed with the nparACT package. In our periodogram analysis of time series data we will use Fast Fourier Transform Non-linear Least Squares (FFT-NLLS), a nonlinear least-squares algorithm of a times series typically used for luminescence data (149) and analyzed with Biodare software (150). Data will be presented as mean  $\pm$  SEM for variables that can be considered normally distributed (or median and range for variables not normally distributed). All analyses will use R (v.3.2.5), Biodare 2, and SPSS (SPSS Inc., Chicago, IL).

**Inclusion Criteria:** *Study will include individuals that are;*

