**Figure 1. Outcome Measures**

Aims	Outcome Measure	Test	Assessment	Statistical Test
Aim 1	Primary	Phase Angle of entrainment (DLMO – sleep onset)	Baseline	ANOVA
			Misalignment	
	Secondary	Clock gene expression in PBMCs	Baseline	Cosinor Analysis, Mixed Model ANOVA
			Misalignment	
Aim 2	Secondary	Urinary Melatonin	Baseline	Wilcoxon signed-rank test
			Misalignment	
	Exploratory	Clock gene expression and Per2::LUC in Colonic Organoids	Baseline	Cosinor Analysis, FFT-NLLS
			Misalignment	
Aim 2	Primary	Intestinal Permeability (i.e. 12-24 h Urinary Sucralfate)	Baseline	Mann-Whitney U test
			Misalignment	
	Secondary	Mayo Score (Endoscopy)	Baseline	Wilcoxon signed-rank test
			Misalignment	
	Secondary	Stool Calprotectin	Baseline	Wilcoxon signed-rank test
			Misalignment	
Aim 2	Secondary	Serum cytokines (IL-6, TNF- $\alpha$ )	Baseline	Repeated measures ANOVA
			Misalignment	
	Secondary	Fecal Microbiota	Baseline	Principal Coordinate Analysis
			Misalignment	
Aim 2	Secondary	Serum LBP, LPS, zonulin, sCD14, metabolomics	Baseline	Repeated measures ANOVA
			Misalignment	
	Exploratory	TER in 2D Colonic	Baseline	ANOVA

		Organoids with ex-vivo TNF- $\alpha$ /INF- $\gamma$	Misalignment	
Exploratory		RNA seq of Colonic Organoids	Baseline	JTK Cycle
			Misalignment	

**Safety and Adverse Events:** We have identified five key potential risks to human subjects in this study:

1. Risk to Confidentiality and Record-Keeping of patient personal health information (PHI).
2. Risk of potential side effects associated with Phlebotomy (blood draw).
3. Risk of potential side effects associated with Sigmoidoscopy and Colonic Biopsy.
4. Risk of potential side effects associated with completion of the Questionnaires.
5. Risk of potential side effects associated with in lab study

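### Calprotectin, endoscopic score and urinary melatonin have no named test of whether UC patients change more than controls

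*Combined protocol and SAP*

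**What the plan says.** The Abstract frames the study as a test of whether "UC patients (compared to healthy subject controls) are less resilient to circadian misalignment". Its Aim 2 hypothesis is that "circadian misalignment will increase colonic permeability and mucosal inflammation in UC patients (vs. Controls", and the measures follow at once: "vs. Controls) (Aim2) through the following: endoscopy score, stool calprotectin". The Specific Aims section is narrower: there Aim 2 concerns the effect of misalignment within UC and mentions no comparator.

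In Figure 1 (Outcome Measures), the rows for urinary melatonin, Mayo Score (Endoscopy) and stool calprotectin each list Baseline and Misalignment as assessments and name one test, the "Wilcoxon signed-rank test". Other rows use other tools: "Mann-Whitney U test" for intestinal permeability, "Repeated measures ANOVA" for serum cytokines and for LBP, LPS and related markers, and a mixed-model ANOVA for clock genes in PBMCs.

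The Sample Size Analysis section says the investigators "will use the Wilcoxon match-pair test for analysis of colonic permeability, inflammatory cytokines, and markers of endotoxemia". That sentence covers none of the three outcomes and does not define the pair. A further sentence mentions ANOVA and linear regression with order effects as a covariate. It names no endpoint, no group term and no group-by-condition term. On error rates the section says "we assume a Type I error rate of 0.05 and a 2-sided test for all analyses".

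Study Outcomes lists the Mayo Endoscopic Score among the primary measures for Aim 2; Figure 1 lists it as secondary.

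**The concern.** A paired test across the two test days asks whether values moved. The Abstract asks whether they moved more in UC than in controls. Run in each group separately, or once in all 40 subjects, the signed-rank test contains no comparison of the groups.

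The control group matters here because the sequence is fixed. Under Procedures, every subject has Test Day 1 (baseline) before Test Day 2 (misalignment) in the same stay. Within one group, a change therefore mixes misalignment with elapsed time, confinement in the laboratory and an earlier sigmoidoscopy with 19 biopsies. Order cannot be separated from condition within subjects. Controls go through the same sequence, so contrasting the two groups' changes removes whatever is common to both. These three rows do not use that contrast.

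At stake is a report of UC-specific inflammation when both groups changed by the same amount.

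**Working it through.** **Inputs from the documents.** 20 UC and 20 controls (Research Design); two-sided alpha 0.05 (Sample Size Analysis); each subject measured at baseline and after misalignment. No sample size, power or SD of change is stated for the three outcomes, so there is no plan figure to reproduce.

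**Assumptions.** Change scores are normal, with the same true mean change in both groups, from 0 to 1.0 SD of the change score. There were 20,000 simulated studies per setting.

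**Step 1: inferring a group difference from two separate tests.** If each group's signed-rank test is significant with probability p, and the groups are independent, then

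P(UC significant, controls not) = p × (1 − p).

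This peaks at 0.5 × 0.5 = 25%. Simulated results:

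| Common true change (SD) | p in one group | p × (1 − p) | Simulated: UC significant, controls not | Mann-Whitney on change |
|---|---|---|---|---|
| 0 | 0.052 | 4.9% | 5.0% | 5.0% |
| 0.3 | 0.236 | 18.0% | 18.1% | 4.9% |
| 0.4 | 0.378 | 23.5% | 23.2% | 4.7% |
| 0.5 | 0.546 | 24.8% | 24.7% | 4.7% |
| 0.6 | 0.702 | 20.9% | 21.4% | 4.8% |
| 0.8 | 0.912 | 8.0% | 8.2% | 5.0% |
| 1.0 | 0.984 | 1.6% | 1.5% | 4.8% |

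A signed-rank test on matched UC-minus-control differences in change stays between 4.4% and 5.1% across the settings run.

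**Step 2: what a direct comparison can detect.** By normal approximation, for 80% power at two-sided 0.05:

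- Between groups: (1.960 + 0.842) × √(2/20) = 2.802 × 0.316 = 0.89 SD of the change score.
- Within one group of 20: 2.802 / √20 = 0.63 SD.

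**Step 3: endoscopic score.** The signed-rank test ranks only non-zero differences. If controls score 0 on both days (an expectation, since GI disease excludes them; the documents do not state it), there is nothing to rank in that group. In UC, five non-zero changes in one direction give an exact p of 2 × 0.5⁵ = 0.0625, and six give 2 × 0.5⁶ = 0.031. Fewer than six non-zero changes cannot reach 0.05. With exactly six, all must agree; with more, unanimity is not required.

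**The case against.** **The formal aim is within UC.** Specific Aims words Aim 2 without controls, and Sample Size Analysis ends by applying its power to UC patients before and after the night shifts. A within-subject test answers that question. This stands, and it limits the point: the mismatch is with the Abstract. The Abstract's comparator wording for Aim 2 attaches to endoscopy and calprotectin. For urinary melatonin the group comparison comes only from the general statement about resilience, and that outcome is missing from the secondary outcome list in Study Outcomes.

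**The pair might be a UC patient and a matched control.** Subjects are matched on age, sex, race and BMI, and no sentence defines the pair, so this reading is not excluded. The Baseline and Misalignment layout and the described within-subject design make it the less likely one. If it is intended, the plan has to say so and say that the quantity compared is change.

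**A reader might infer a decision rule.** It is tempting to say that the plan will claim a UC effect because UC is significant and controls are not. The documents contain no such rule. They give no rule at all for the group claim.

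**A reader might quote 18% to 25% as the error rate.** Those values belong to assumed effects between 0.3 and 0.6 SD. The rate is about 5% with no change and 1.5% at 1.0 SD.

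**A reader might extend the point to the serum markers.** Repeated-measures ANOVA can carry a group-by-condition term, so the same gap is not shown there. An argument that missed draws would remove many subjects needs an assay schedule and a missing-data rate, and the documents give neither. Only the conflict between Sample Size Analysis and Figure 1 remains. Nor does the PBMC row already supply the needed term: it names a mixed-model ANOVA without stating an interaction.

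**Conclusion.** The point holds in a limited form. For three outcomes, the only named test cannot, on its most natural reading, address the UC-versus-control hypothesis in the Abstract, and no other section supplies a group comparison of change. This is more than missing detail, because a test is stated and it answers a different question.

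The size depends on how the group claim would be made. Two separate significance results would give the false-claim rates tabulated above, at most about 25%; a direct test would hold about 5%. Those rates rest on assumed effect sizes, normal change scores and equal true change in the two groups. The structural finding needs none of these assumptions. The endoscopic score deserves particular attention because the plan lists it as both primary and secondary.

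**What to change.** 1. **Calprotectin and urinary melatonin.** Make the UC-versus-control test a comparison of Test Day 2 minus Test Day 1 change on the log scale. Choose one method in advance: Mann-Whitney on change, a signed-rank test on the matched UC-minus-control difference in change, or a mixed model with a group-by-condition term. Keep the within-group signed-rank tests as description.
2. **Endoscopic score.** If controls score 0 on both days as expected, report the change in UC only and draw no UC-versus-control conclusion from it. Reconcile its primary listing in Study Outcomes with its secondary listing in Figure 1.
3. **Aim 2 wording.** Align the Abstract and Specific Aims on whether the claim is within UC or against controls.
4. **Serum cytokines and endotoxemia markers.** Reconcile the matched-pair Wilcoxon test in Sample Size Analysis with the repeated-measures ANOVA in Figure 1, and state the group-by-condition term.

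No new data are needed; the cost is a few rows of Figure 1 and the matching sentences. The real price is power: with 20 per group, 80% power needs a difference in change of about 0.89 SD, against about 0.63 SD for a change within one group. Some results that would look positive within UC will not support a group claim.

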**Ulcerative Colitis:**

1. Patients with other forms of colitis such as Crohn's disease (CD) or indeterminate colitis
2. Patient with active UC (Mayo  $> 2$ )
3. Pancolonic UC (colitis past the splenic flexure, Montreal E3))
4. Gastrointestinal surgery
5. Other GI diseases or systemic diseases (cardiac, renal failure, cirrhosis)
6. Shift work in the last 6 months
7. Antibiotic use within last 12 weeks
8. Patients who have used anti-diarrheal agents such as Lomotil or Imodium within 3 days of the study
9. Prednisone use the last 30 days
10. Significant Depression (score  $\geq 14$  BDI)
11. Significant Anxiety (score  $\geq 40$  STAI)
12. Use of probiotic supplement in last 4 weeks except yogurt.
13. Intentional change in diet.

14. Chronic use of NSAIDS. A washout period of 3 weeks is needed before the subject could be enrolled into the study. Low dose aspirin is allowed.
15. Chronic Alcohol use. A washout period of 3 weeks is needed before the subject could be enrolled into the study.
16. Have children under 6 months

**Subject Recruitment:** All Human UC subjects will be recruited at the RUMC Digestive Disease Clinic and the Rush Crohn's and Colitis Center by the PI or Clinical Coordinator. Healthy control subjects will be recruited by established recruiting methods, which we have successfully used over the past ten years, including notices to local organizations and internet, newspaper, and radio advertising. Based on our experience, of the initial calls made by potential subjects, 15% remain interested in the study after they are informed of study procedures. Of these individuals, 70% pass an initial telephone screening (in which questions are asked about medical condition, current medication use and work and travel history). Of those remaining individuals, 33% pass the medical and psychological screening (described below), and of these, 70% complete the study.

In this study we will recruit 40 Human Subjects in the following two groups:

- 1) Ulcerative Colitis (UC) (n=20).
- 2) Healthy Controls (HC) (n=20).

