All experimental procedures will commence after admission to the CCC for a 7 day in-lab evaluation. The sleep episode will be the same as that maintained during the 2 weeks prior to the in-lab phase assessment. On Test Day 1 (TD1, Baseline alignment), at 0900h all subjects will have a unprepped flexible sigmoidoscopy (FS) with rectal biopsy collection (19 biopsies, ~15 cm from the anal verge), after which intestinal permeability will be assessed (24h urine collection after ingestion of a sugar cocktail: sucrose, mannitol, lactulose, sucralose103), and every 2 hour blood sampling during/surrounding standardized meals (primary and secondary outcomes for Specific Aims 1 & 2). During the last 8h of the phase assessment, subjects will be exposed to a background illumination ~3 lux to assess the endogenous circadian phase through hourly plasma melatonin (dim light melatonin onset, DLMO). On Protocol Day 3, subject behavioral cycles will be shifted by 12h, and this schedule will be maintained until Protocol Day 7. Following the short 4h sleep episode on Day 3, subjects will have 3 “night shift” days (Days 3-5). The 12h shift on Day 3 will be achieved by including an 8h wake episode and a 4h sleep opportunity, thereby maintaining the same sleep opportunity-to-wake ratio (1:2). The rationale for the 12h inversion of the sleep-wake timing is that we previously found that the influence of circadian misalignment on physiological variables are maximal when the sleep/wake and fasting/feeding cycle was shifted by ~12h relative to the endogenous circadian timing system. On Test Day 2 (TD2, Circadian misalignment), all subjects will have all the identical tests conducted as described on TD1; however, the FS and start of repeated measures will be at 2100 h – matched to the sleep/wake cycle and not clock time to isolate the impact of circadian misalignment. 24 hours prior to each flexible sigmoidoscopy, stool will be collected from subjects. Discharge from the lab will be on day 7 after an 8h sleep period. We will test for order effects (see Statistics).

**Blood draw.** Blood (30 cc) will be drawn in endotoxin free tube and serum then immediately separated and stored in -80°C freezer until measurement for Serum endotoxin (END). Blood will also be drawn for CBC, comprehensive biochemical profile [CMP that includes

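### Two different tests are named for the same serum inflammation and endotoxemia markers with no rule for choosing, and a before/after Wilcoxon test cannot compare the UC response with that of controls

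*Combined protocol and SAP*

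**What the plan says.** Figure 1 (Outcome Measures) has two secondary Aim 2 rows for serum markers. One covers the cytokines IL-6 and TNF-α; the other is "Serum LBP, LPS, zonulin, sCD14, metabolomics". Both carry "Repeated measures ANOVA", and both list only Baseline and Misalignment as assessments.

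The Sample Size Analysis expects non-normal data and assigns a "Wilcoxon match-pair test for analysis of colonic permeability, inflammatory cytokines, and markers of endotoxemia". It then mentions ANOVA and linear regression, to be used where appropriate, without tying either to these markers.

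On sampling, Procedures calls for "every 2 hour blood sampling during/surrounding standardized meals" on each test day and links this in general terms to the primary and secondary outcomes of both aims. The separate Blood draw paragraph describes the endotoxin sample without giving a number of time points. For another blood-based outcome, clock genes in PBMCs, Figure 1 names "Cosinor Analysis, Mixed Model ANOVA".

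The documents contain no missing-data rule for these markers, no per-subject summary (24-h mean, area under the curve, peak), no covariance structure and no sphericity correction.

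**The concern.** The two entries are different analyses of the same data. They can give different answers, and whoever runs the analysis may choose after seeing the results.

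They also answer different questions. The Abstract frames Aim 2 as an effect of misalignment in UC patients set against controls, and it lists systemic barrier and inflammation markers under Aim 2a. A signed-rank test of baseline against misalignment asks only whether a group changed. A change in UC and no detectable change in controls would not show that the two groups differ.

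Repeated measures ANOVA with group as a between-subject factor does ask the right question. In its classical form, though, it needs a complete set of values per subject and normal residuals. Subjects who leave before the second test day would drop out of the systemic inflammation and barrier evidence for Aim 2, which costs precision and favours those who tolerate the protocol.

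**Working it through.** **1. The two entries side by side.** The plan gives no power or effect size for these markers, so there is no figure to reproduce.

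| Marker | Sample Size Analysis | Figure 1 |
|---|---|---|
| IL-6, TNF-α | Wilcoxon matched pairs | Repeated measures ANOVA |
| LPS, LBP | Wilcoxon matched pairs (as endotoxemia markers) | Repeated measures ANOVA |
| Zonulin, sCD14 | Covered only if counted as endotoxemia markers | Repeated measures ANOVA |

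The conflict is certain for the cytokines. For LPS it follows from Background A.3, which defines endotoxemia by systemic LPS. LBP is grouped with LPS in the secondary outcome list. For zonulin and sCD14 it depends on how broadly the text is read.

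**2. What each test can estimate.** Write Y(i,B) and Y(i,M) for subject i at baseline and misalignment, and D(i) = Y(i,M) − Y(i,B).

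- Before/after Wilcoxon: tests whether D is centred on zero within a group, with one D per subject.
- Aim 2 contrast: mean D in UC minus mean D in controls, that is, group by condition.

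The first does not contain the second. If several draws per day exist, they must be collapsed before a Wilcoxon test. Pooling 12 time-point pairs per subject as though independent gave a simulated type I error of about 27%, against 5% with one summary per subject (20 subjects; assumed subject-level SD 0.5, residual SD 1).

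**3. How many subjects a complete-case ANOVA keeps.** Expected complete cases per 20 = 20 × (1 − m)^k, with k assayed draws per subject and miss rate m. The documents give neither. The calculation assumes independent misses and is an illustration only.

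| m (assumed) | k = 2 (one value per test day) | k = 24 (12 two-hourly draws on each of two days) |
|---|---|---|
| 1% | 20 × 0.980 = 19.6 | 20 × 0.786 = 15.7 |
| 2% | 20 × 0.960 = 19.2 | 20 × 0.616 = 12.3 |
| 5% | 20 × 0.9025 = 18.1 | 20 × 0.292 = 5.8 |

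Misses are likely to cluster in the same people (difficult veins, early departure). With an assumed intraclass correlation of 0.1 to 0.3 and k = 24, 78% to 88% stay complete at m = 2% (62% if independent), and 54% to 73% at m = 5% (29% if independent).

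**4. What a replacement model must contain.** Suppose 12 draws per test day, residual SD 1, and a subject-by-condition SD of s. The variance of one subject's mean for one condition is s² + 1/12. A model with only a subject random intercept treats it as 1/12. The ratio is 1 + 12s²:

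- s = 0.3: 1 + 12 × 0.09 = 2.08
- s = 0.5: 1 + 12 × 0.25 = 4.00

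The variance behind the group by condition test is thus about 2 to 4 times too small. Simulation under no true difference (20 per group) gave type I error of 16% and 29% for these two values. With within-day autocorrelation of 0.3 or 0.5 instead, it was 14% or 24%. It was 5% only with neither present. All variance values are assumed.

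**The case against.** **The tests may be complementary.** The Sample Size Analysis speaks of UC patients before and after the simulated shifts, which a Wilcoxon test suits, and repeated measures ANOVA could supply the group comparison. A Wilcoxon test on differences in change within matched UC–control pairs would also address Aim 2. Each arrangement is possible, but the plan sets out none of them, so the conflict is narrowed and not removed.

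**The repeated series is an inference.** A reader might conclude that every marker is assayed every 2 hours, so that one missed draw deletes a subject and only 79%, 62% or 29% remain at 1%, 2% or 5% missed draws. The documents do not support this as fact. The 2-hourly blood also serves other outcomes, such as PBMC clock genes; Figure 1 shows two assessments; no missing-data rule or software routine is named; and independent misses are implausible. With one value per condition, the Wilcoxon test ignores no time series and sphericity is automatic with two levels. This objection stands.

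**Completion.** Subject Recruitment reports that "of these, 70% complete the study". Reading this as 0.70 × 40 = 28 completers is tempting, but the plan does not say whether 40 counts those enrolled or those who finish. The number with both test days could lie anywhere from 28 to 40.

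**The PBMC row.** It may be read as proof that the plan already has a better method. Its label could equally mean a mixed-design (between–within) ANOVA, which can share the complete-case limitation.

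**Conclusion.** The point holds in a limited form. The same secondary markers have two different tests and no rule of precedence. A before/after Wilcoxon test does not address UC against controls. Repeated measures ANOVA can, but in its classical form it fits poorly with the plan's own expectation of non-normal data, and it drops subjects lacking a test day.

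The inconsistency and the mismatch with Aim 2 rest on the text alone. The size of any loss does not. It is small with one assayed value per test day (18.1 to 19.6 of 20 kept at 5% to 1% missed). It is possibly large with a fully assayed series, under assumptions the documents neither state nor exclude. Loss of any subject with a single missed draw, and any claim that Figure 1's test cannot compare the groups' responses, should not be read into the plan.

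This concerns secondary outcomes and should be corrected before analysis.

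**What to change.** In the Sample Size Analysis and in Figure 1, name one analysis for IL-6, TNF-α, LBP, LPS, zonulin and sCD14, and remove the Wilcoxon and repeated measures ANOVA entries for them:

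- A linear mixed model on log-transformed values, fitted by REML to all available data.
- Fixed effects for group, condition and group by condition, the last being the key test.
- Random effects for subject and matched pair.
- A statement of which time points are assayed for each marker.
- If more than one draw per test day is assayed: add time since waking, condition by time, and a subject-by-condition random effect (or within-day autocorrelation). Procedures aligns the two test days by sleep/wake cycle, so the same time since waking falls at a different circadian phase; this is why condition by time is needed. Group by condition is then tested as the average over the day.
- A simpler alternative is one pre-specified 24-h summary per subject and condition in the basic model. With complete draws this is equivalent; with missed draws it needs a rule for computing the summary.

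Metabolomics shares a Figure 1 row with the serum markers, so that row should be split. The permeability part of the Wilcoxon sentence is outside this point.

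The cost is wording in one section and two table rows. R and SPSS, already named, fit the model, and no new data are required. The downsides are an assumption of normal residuals on the log scale, which should be checked, and slightly more modelling work. Subjects with only the first test day stay in the model but add little to the within-subject contrast.
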